Statistical Analysis Plan Version 2.0, 27 February 2024

1 Abbreviations

 $\begin{array}{ll} \alpha SYN & Alpha-synuclein \\ A\beta & Amyloid \ beta \end{array}$

AD Alzheimer's disease

ADAS-Cog Alzheimer's Disease Assessment Scale-Cognitive Subscale

ADCS-ADL Alzheimer's Disease Cooperative Study—Activities of Daily Living Scale

ADCS-CGIC Alzheimer's Disease Cooperative Study—Clinical Global Impression of

Change

AE Adverse Event

APP Amyloid β Precursor Protein AR(1) First-order Autoregressive

ATC Anatomical Therapeutic Chemical

AUC Area under the curve

C_{max} Maximum plasma and CSF concentration

CI Confidence interval

CL Clearance

CM Concomitant medication
CSF Cerebrospinal Fluid
CSP Clinical Study Protocol

C-SSRS Columbia Suicide Severity Rating Scale

CV Coefficients of variation

DSMB Data Safety Monitoring Board
DSST Digital Symbol Substitution Test

ECG Electrocardiogram

eCRF Electronic Case Report Form

ES Enrolled set

FDA Food and Drug Administration
GFAP Glial Fibrillary Acidic Protein

IC Informed Consent

IMP Investigational Medicinal Product iSAP interim Statistical Analysis Plan

ITT Intent-to-Treat set
LSM Least Square Mean
MAR Missing at Random

MCMC Markov Chain Monte Carlo

MedDRA Medical Dictionary for Regulatory Activities

mITT Modified Intent-to-Treat set

MMRM Mixed Model for Repeated Measures

MMSE Mini-Mental State Examination

MNAR Missing Not at Random NFL Neurofilament Light Phosphorylated tau p-tau PDParkinson's disease PΚ Pharmacokinetic PPS Per-protocol set PT Preferred Term QD Once a Day

SAE Serious Adverse Event
SAF Safety analysis set
SAP Statistical Analysis Plan
SD Standard Deviation
SOC System Organ Class

TEAE Treatment-Emergent Adverse Event

T_½ Half-life tau Tau protein

TDP-43 TAR DNA-binding Protein 43 t_{max} Time to peak drug concentration

TOEPH Heterogeneous Toeplitz

UN Unstructured

WHO World Health Organization

2 Document Version History

Version Number	Version date	Section(s) Updated	Change since previous version (with reason)
Final 1.0	16-JAN-2024	All	Final version
Final 2.0 Amendment	27-FEB-2024	Section 8.8	Missing data algorithm was added on item scores of co-primary endpoint ADAS-Cog11 as a sensitivity analysis

3 Introduction

This Statistical Analysis Plan (SAP) is based on Clinical Study Protocol (CSP) Version 3.1, dated September 25, 2023. In the case where there is a difference between the protocol and the SAP, the SAP will be the ruling document.

Currently, there is no treatment available to stop or reverse the progression of Alzheimer's (AD) and Parkinson's disease (PD). Neurodegenerative diseases such as AD and PD share many common characteristics, including the central role of neurotoxic aggregating proteins in their pathogenesis. Amyloid β (A β) and tau aggregates (senile plaques and neurofibrillary tangles, respectively) have been traditionally associated with AD, while alpha-synuclein (α SYN) aggregates (Lewy bodies) have been associated with PD. However, it is becoming increasingly clear that all these proteins are involved in both diseases and that aggregation of one can lead to accumulation of another. Furthermore, in several studies of brains from older AD participants, a high percentage of all AD brains present mixed pathologies, such as Lewy body disease. Several clinical trials targeting just one (often A β) of the neurotoxic aggregating proteins have failed. Finally, other fragments of Amyloid β Precursor Protein (APP) have been implicated in AD pathology. Collectively, these facts point to the need for lowering multiple neurotoxic aggregating proteins simultaneously, if we are to have a good chance of at least halting disease progression.

Buntanetap has a unique mechanism of action, in that it inhibits the translation and, therefore, reduces the levels of several neurotoxic aggregating proteins both *in vitro* and *in vivo*, including α SYN, APP, its fragments, and tau. Although APP and its downstream products (Ab oligomers, c-terminus peptide, and amyloid plaques), and tau neurofibrillary tangles have been well documented to be culprits of AD, recent research has shown that other misfolded proteins are also part of the equation. For example, increased levels of α SYN and TAR DNA-binding protein 43 (TDP-43) have been shown to be correlated with deficits in cognitive functions in AD participants. Therefore, it is reasonable to hypothesize that inhibiting expression of all the above neurotoxic proteins should lead to a better efficacy outcome in AD participants than inhibiting just one.

The objective of this study is to assess efficacy and safety of buntanetap in participants with mild to moderate AD. We only tested 80 mg once daily (QD) in Phase 2a study in AD participants. During the dose-finding Phase 2a PD study, a dose-response curve between 0 and 80 mg QD was observed with 10 and 20 mg QD showing the best benefit. Therefore, we want to do a similar dose-ranging trial to test the efficacy of 7.5 mg, 15 mg and 30 mg QD buntanetap.

4 Study Objectives and Endpoints

Objective Endpoint

Primary

The primary objective is to assess efficacy and safety of buntanetap in participants with mild to moderate AD.

1. Alzheimer's Disease Assessment Scale-Cognitive Subscale 11 (ADAS-Cog 11)

Change in ADAS-Cog 11 from Baseline to Week 12.

ADAS-Cog 11 is an 11-item score measuring cognitive functions and non-cognitive functions such as mood and behavior. Total scores range from 0-70, with higher scores indicating greater cognitive impairment.

2. Alzheimer's Disease Cooperative Study-Clinical Global Impression of Change (ADCS-CGIC)

ADCS-CGIC is a validated categorical measure of change in the participant's clinical condition between baseline and follow-up visits. It measures whether the effects of active treatment are substantial enough to be detected by a skilled and experienced clinician on the basis of a clinical interview and examination. It relies on both direct examination of the participant and an interview of the study partner. A skilled and experienced clinician who is blinded to treatment assignment rates the participant on a 7-point Likert scale, ranging from 1 (marked improvement) to 7 (marked worsening). Lower scores indicate better improvement.

3. Safety and tolerability

- Adverse events (AE)
- Severity of AEs
- Drug related AEs
- · AEs leading to study discontinuation
- Electrocardiogram (ECG) findings
- Clinical laboratory test results
- Vital sign measurements
- Physical examination findings

Objective

ANVS-22002

Endpoint

Secondary

Assess improvement on AD participants' daily living and cognitive functions

Alzheimer's Disease Cooperative Study-Instrumental Activities of Daily Living Scale (ADCS-ADL)

The ADCS-ADL is a 23-item inventory developed as a rater-administered questionnaire answered by the participant's study partner. The ADCS-ADL measures both basic and instrumental activities (instrumental activity items 6a, 7-23) of daily living by participants with a lower score indicating greater severity.

2. Mini Mental State Examination (MMSE) Score

MMSE is a brief screening instrument used to assess cognitive function (orientation, memory, attention, ability to name objects, follow verbal/written commands, write a sentence, and copy figures). Total score ranges from 0 to 30 with a lower score indicating greater disease severity.

3. Digital Symbol Substitution Test (DSST)

In the DSST individuals are asked to record associations between different symbols and numbers within time limits. The total score is the sum of all the correctly coded numbers and higher scores indicate better performance.

Exploratory

Investigate change after buntanetap in potential biomarkers

1. Plasma biomarkers

Potential biomarkers to be measured in plasma are A β 42/40 ratio, phosphorylated tau 181 (pTau181), pTau217, Neurofilament Light (NFL), Glial fibrillary acidic protein (GFAP) and TAR DNA-binding protein 43 (TDP43).

2. Pharmacokinetics (PK) Analysis

The following PK parameters will be determined: Area under the curve (AUC), C_{max} , T_{max} , $t_{1/2}$, and CL.

ANVS-22002

5 Overall Study Design

This is a 12-week randomized, double-blind, placebo-controlled, dose-ranging, multicenter clinical trial investigating the efficacy, safety, and tolerability of three different doses of buntanetap or placebo in participants with mild to moderate AD.

Qualified participants will be randomly assigned at a 1:1:1:1 ratio to one of the four treatment arms: buntanetap 7.5 mg, buntanetap 15 mg, buntanetap 30 mg, and placebo after a screening period of up to 42 days.

ADAS-Cog 11, ADCS-CGIC, ADCS-ADL, DSST, and MMSE will be assessed by clinicians who have successfully completed the requisite certifications/trainings for each assessment. All efforts will be made to ensure participants will be assessed by the same clinician throughout the study.

320 mild to moderate AD participants will be randomized to 7.5 mg, 15 mg, 30 mg of buntanetap QD or placebo.

Participants who have signed an informed consent and meet screening eligibility requirements will be randomly assigned at a 1:1:1:1 ratio to one of the four treatment arms: buntanetap 7.5 mg, buntanetap 15 mg, buntanetap 30 mg, and placebo, through an Interactive Randomization System, after a screening period of up to 42 days, followed by an at home dosing period of 12 weeks. Participants will be required to visit clinics at Day 0 (baseline), 6 weeks, and 12 weeks (end-of-trial), where they will undergo study procedures that include safety assessments (AE and concomitant medication monitoring, 12-lead ECGs, clinical laboratory testing, vital signs assessments, and physical/neurological examinations), and psychometric tests (ADAS-Cog11, ADCS-CGIC, ADCS-ADL, DSST, MMSE).

The Schedule of Events is shown in Appendix 1.

6 Determination of Sample Size

A sample size of up to 320 participants (1:1:1:1 randomized to 7.5 mg, 15 mg, 30 mg buntanetap and placebo respectively) is planned to be randomized.

Qualified participants will be randomized at a 1:1:1:1 ratio to one of the following four treatment groups: 7.5 mg, 15 mg, 30 mg QD buntanetap and placebo. A sample size of 280 (210 combining all three buntanetap-treatment groups and 70 in control) will have 90% power to detect a treatment difference for the co-primary efficacy variable ADAS-Cog11 at a two-sided significance level of 0.05, assuming a delta of 2.7 between the treatment (pooling all three treatment arms together) and placebo, and a common standard deviation (SD) of 6.0. This sample size will also have an 89% power to detect a significant difference for the co-primary efficacy variable ADCS-CGIC at a two-sided significance level of 0.05, assuming a delta difference 0.23 between the treatment (pooling all three treatment arms together) and placebo, and a common SD of 0.5. Approximately 320 participants will be randomized (approximately 80 per arm) to account for an expected 12.5% dropout rate.

7 Data Sets to be Analyzed

The following analysis sets will be used for the statistical analysis and presentation of data:

- The Enrolled analysis set (ES) will include all participants who signed IC and meet all inclusion
 and exclusion criteria. All data collected from ES will be presented in listings and if relevant in
 tables and/or graphs. Screening failures will have selected data be presented in a separate
 listing if needed.
- The Intent-to-Treat set (ITT) will consist of all participants who are randomized. The primary
 efficacy analyses will be based on the ITT.
- The Modified Intent-to-Treat set (mITT) will consist of all participants who are randomized, receive at least one dose of study drug, and have both a baseline and at least one postbaseline assessment value for the ADAS-Cog11 or ADCS-CGIC score after taking study drug. The mITT will be used to support the primary efficacy analyses.
- The Safety analysis set (SAF) will consist of all randomized participants who receive at least one dose of study drug. The safety analyses will be based on the SAF.

- The Per-protocol set (PPS) will consist of all participants in the mITT who complete at least 67 days treatment exposure (Last dose date - First dose date + 1 >= 67 days) without any major protocol deviations that potentially could impact the primary efficacy endpoint. The membership of this analysis set will be determined prior to database lock. The PPS will be used to support the primary and secondary endpoints as supportive analyses.
- The PK set will analyze all available data from safety participants receiving buntanetap and with at least one sampling profile allowing derivation of at least one PK parameter.

Protocol deviations leading to exclusions from PPS include but are not limited to the following:

- Non-fulfilment of all inclusion criteria
- Fulfilment of at least one exclusion criterion
- Use of certain concomitant medications (for details see section 8.3.11)

The final criteria for the PPS, regarding which protocol deviations that warrant exclusion, will be determined before breaking the blind.

Baseline presentations will be based on the SAF.

Safety presentations will be based on the SAF.

Exposure to study drug will be given for the SAF.

The ITT and mITT will be analyzed according to randomized (planned) treatment. Safety and PPS will be analyzed on actual treatment.

Plasma concentration-time data for buntanetap will be based on the SAF. PK parameters derivations and statistical analyses are described in a separate PK SAP and will be based on the PK set (see Section 8.5).

8 Statistical and Analytical Plans

8.1 **Changes to the Planned Analyses**

There have been no changes in the planned analyses in the study protocol.

8.2 **Hypothesis and Statistical Methods**

For tests of statistical significance on efficacy variables the significance level (p-value) will be provided together with the 95 percent confidence intervals (CI) of the mean, minimum, median, first and third quartiles and maximum.

[figure not shown]
Level of Significance, Multiple Comparisons and Multiplicity 8.2.1

The primary study hypothesis is that buntanetap-treatment (pooling three treatment arms together) is superior to placebo in reducing the cognitive impairment and function impairment of AD participants, as assessed by the two co-primary endpoints: change from baseline in the ADAS-Cog11 score at 12week and ADCS-CGIC score at 12-week. The two co-primary endpoints will be tested at a two-sided significance level of 5% without multiplicity adjustment. If both test hypotheses are rejected at the 5% level, the test will continue onto secondary endpoints in a hierarchical testing order, at a two-sided significance level of 5%. If one of the two co-primary endpoints is not statistically significant, the hypothesis testing for all subsequent endpoints will be considered exploratory.

To control for study-wise type 1 error rate, a fixed-sequence hierarchical testing procedure will be applied to adjust for multiplicity arising from multiple secondary endpoints. The hierarchical testing order for the secondary endpoints are:

- 1. ADCS-ADL
- 2. MMSE score
- 3. DSST

This hierarchical testing process is presented graphically below:

The study is also designed to explore the effectiveness of three buntanetap-treatment dose level. Nominal p-values will be provided for these test hypotheses of each dose arm vs. placebo, without multiplicity adjustment.

All other exploratory endpoints are considered supportive and no adjustment for multiplicity will be applied.

8.2.2 Definitions

Treatment- Emergent Adverse Event	Treatment emergent adverse events (TEAEs) are defined as undesirable events not present prior to medical treatment, or an already present event that worsens either in intensity or frequency following the treatment. If an AE starts at the same day as the study drug the start time of the AE will be compared with the start time of the administration of study drug. If the start time of the AE is at or after start time of administration of study drug the AE is a TEAE. If no clear assignment is possible due to incomplete or missing start dates, the AE will be counted as TEAE.
Baseline	Baseline will be the last assessment before or up to the first dosing of the study drug. This is valid for vital sign, laboratory data, and safety data, where a difference from baseline is derived. For diary data and questionnaire data, baseline will be the assessment at the baseline visit.
Height [cm]	All values collected in inches will be converted to cm as follows: Height [cm] = height [feet] * 30.48
Weight [kg]	All values collected in pounds will be converted to kg as follows: weight [kg] = weight [pounds] * 0.454

Relative day	The relative day of an event is derived as:
	Relative day = (Start date) - (Date of first administration of Investigational Medicinal Product (IMP) + 1
	For events occurring or starting before the date of first administration of IMP, the relative day is derived as:
	Relative day = (Start date) - (Date of first administration of IMP)
	In this way, there will be no Day 0. Day 1 is the same day as the day of first administration of IMP, and Day -1 is the day before.
Date format	All dates in analysis datasets and tables, listings and figures will be in the format YYYY-MM-DD

8.2.3 Summary Statistics

Data will be summarized by means of summary statistics. Summary statistics will be provided for the variables described in the following sections.

Categorical data will be presented as counts and percentages, i.e., n (xx.x%). Percentages will be based on the number of subjects in the analysis data set used and given as integers. Zero frequencies will be given without percentages.

For continuous variables, these statistics will include the number of subjects, mean, SD, median, minimum, and maximum.

All variables will be analyzed descriptively with appropriate statistical methods: categorical variables by frequency tables (absolute and relative frequencies) and continuous variables by sample statistics (i.e., number of observations, mean, SD, 95% CI of the mean, minimum, median, first and third quartiles and maximum). Minimum and maximum values will be displayed as reported.

Since the two co-primary endpoints and secondary endpoints are captured at multiple visits, the method selected to analyze the endpoints, which are treated as continuous, will be a Mixed Model for Repeated Measures (MMRM). For the co-primary endpoint ADAS-Cog11 score and secondary endpoints, MMRM will be applied with change from Baseline score as the response (dependent variable) and with Baseline value as a covariate and treatment, timepoint, treatment-by-timepoint interaction as fixed effects (independent variables). The Model for co-primary endpoint ADCS-CGIC score will include treatment, timepoint, treatment-by-timepoint interaction as the fixed effects. Estimation of parameters will be done by means of Restricted Maximum Likelihood method. The Unstructured (UN) variance-covariance structure will be initially used to explore the variance-covariance matrix across visits. If the algorithm doesn't converge, a heterogeneous Toeplitz (TOEPH) as the covariance matrix will be tried first, and then first-order autoregressive (AR(1)) to achieve convergence. The Kenward-Roger approximation will be used to estimate denominator degrees of freedom. The two-sided 95% CI of the treatment differences will be presented.

The co-primary endpoint ADAS-Cog11 score and secondary endpoints will be analyzed using the model explained above as follows:

```
<Endpoint>= intercept + Base + T + V + T*V,
```

with

Base: baseline score;

T: treatment;

V: post-baseline visit (Week 6, Week 12).

The co-primary endpoint ADCS-CGIC score will be analyzed using the model explained above as follows:

<Endpoint>= intercept + T + V + T*V,

with

T: treatment;

ANVS-22002

V: post-baseline visit (Week 6, Week 12).

Treatment comparisons (pooled Buntanetap-treatment vs. Placebo) will be carried out by means of the contrasts on the treatment factor by visit effect in SAS® Software, using proc mixed. Treatment effects will be estimated by means of Least Square Means (LSM) and 95% CI. Differences between treatments (pooled Buntanetap-treatment – Placebo) will be estimated and resulting 2-sided p-values and associated 95% CI will be presented.

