#### 4.2. Study Overview

**Study population:** The study will be conducted in a diverse population of participants with mild to moderate AD.

**Dose selection**: Qualified participants will be randomly assigned at a 1:1:1:1 ratio to one of the four treatment arms: buntanetap 7.5 mg, buntanetap 15 mg, buntanetap 30mg, and placebo.

**Study Design:** 320 mild to moderate AD participants will be randomized to 7.5 mg, 15 mg, 30mg of buntanetap QD or placebo. If they provide informed consent, they will undergo a Screening Visit, and if they are considered eligible per the inclusion and exclusion criteria, they will proceed to participate in the treatment period. Randomized participants will visit the clinic for the first-time dosing in clinic, followed by an at home dosing period of 12 weeks, with daily administration of 7.5 mg, 15 mg, or 30 mg of buntanetap or placebo. Participants will be required to visit clinics Day 0 (baseline), 6 weeks, and 12 weeks (end-of-trial), where they will

Confidential Page 21 of 57

undergo study procedures that include safety assessments (AE and concomitant medication monitoring, 12-lead ECGs, clinical laboratory testing, vital signs assessments, and physical/neurological examinations) and psychometric tests (ADAS-Cog11, ADCS-CGIC, ADCS-ADL, DSST, MMSE). At the end of blood sampling, the participants will need to stay for a minimum of 1 hour of observation. After all end-of-study procedures are complete, the participant will be discharged to home. A 24-hour follow-up call will occur after all clinical visits to assess the participants current condition and if there are any additional adverse events or questions.

Participants who drop out during the initial 9 weeks at home treatment period will be discontinued and complete an early discontinuation visit as soon as possible following discontinuation. Participants that drop out after the initial 9 weeks will be scheduled for an end of trial visit. If 4 participants are discontinued due to severe adverse events a DSMB safety review will be conducted without interrupting the study.

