#### 10 EARLY TREATMENT/STUDY DISCONTINUATION

The investigators at each site will make every reasonable effort to maximize participant retention. However, if an investigator removes a participant from treatment or study, or if a participant declines further treatment or study participation, an early discontinuation visit will be completed as soon as possible following discontinuation.

Ver. 3.1; 09-25-2023

Participants who discontinue from the study prior to completing all protocol procedures may be replaced in consultation with the Sponsor.

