# **APPENDIX 1: SCHEDULE OF EVENTS**

Study Period	Screening/Baseline  Day -42 to 0		At-Home Treatment		Unscheduled Visit k	Early Discontinuation Visit
Visit Timing			6 weeks ± 7 days	12 weeks ± 7 days (end-of-trial) b		
Procedure	Screening j (up to 42 days before Day 0)	Baseline (Day 0)	Clinic Visit -	Clinic Visit	Clinic Visit	Clinic Visit
Informed consent	X					
Inclusion and exclusion criteria	X	X				
Demography information	X					
Full physical and neurological examination	X	X	X	X	X	X
Height, Weight, BMI	X					
Medical and psychiatric history (includes substance use)	X					
Urine pregnancy test (WOCBP only)	X	X	X	X	X	X
MMSE 	X	X		X		X
ADCS-CGIC		X d	Xe	Xe		Xe
ADAS-Cog11		X	X	X		X
ADCS-ADL		X	X	X		X
DSST		X	X	X		X
C-SSRS	X	X	X	X	X	X
Safety laboratory tests c	X	X	X	X	X	X
12-lead ECG	X	X	X	X		X
Vital signs a	X	X	X	X	X	X

Confidential Page **56** of **57** 

Protocol ANVS-22002 Ver. 3.1; 09-25-2023

Study Period	Screening/Baseline  Day -42 to 0		At-Home Treatment		Unscheduled Visit k	Early Discontinuation Visit
Visit Timing			6 weeks ± 7 days 12 weeks ± 7 days (end-of-trial) b			
Procedure	Screening j (up to 42 days before Day 0)	Baseline (Day 0)	Clinic Visit	Clinic Visit	Clinic Visit	Clinic Visit
Randomization		X				
Genetic sample (ApoE)		X				
Study intervention		X g	$X^h$	$X^{I}$		
Study intervention compliance review			X	X		
AE/SAE review	X	X	X	X	X	X
Concomitant medication review	X	X	X	X	X	X
PK sampling		X		X		
Sampling for blood biomarkers		X		X		
24-hour phone follow-up		X	X	X	X	X

<sup>a Vital sign will include sitting blood pressure, pulse, temperature, respiration rate.

Confidential Page 57 of 57

<sup>b Participants that drop out before the initial 9 weeks of study treatment will complete the Early Discontinuation visit and participants that drop out after the initial 9 weeks of study treatment will complete the End-of-Trial visit.

<sup>c Safety labs should be taken fasted.

<sup>d ADCS-CGIC evaluation only.

<sup>e ADCS-CGIC evaluation and scoring the scale.

g Participants are given one pill during the visit after taking pre-dose (0h) blood samples and the pills for the remaining 6 weeks at the end of the visit.

<sup>h Participants are given pills for the remaining 6 weeks at the end of the visit.

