8.2.8 Secondary Analysis

Secondary efficacy endpoints in this clinical trial are

- Change from baseline to Week 12 in ADCS-ADL
- Change from baseline to Week 12 in MMSE score
- Change from baseline to Week 12 in DSST

Change from Baseline to Week 12 in ADCS-ADL

The ADCS-ADL is a 23-item inventory developed as a rater-administered questionnaire answered by the participant's study partner. The ADCS-ADL measures both basic and instrumental activities (instrumental activity items 6a, 7-23) of daily living by participants with a lower score indicating greater severity.

ADCS-ADL score will be analyzed by MMRM, similar to the co-primary endpoint ADAS-Cog11 score.

Change from Baseline to Week 12 in MMSE Score

MMSE is a brief screening instrument used to assess cognitive function (orientation, memory, attention, ability to name objects, follow verbal/written commands, write a sentence, and copy figures). Total score ranges from 0 to 30 with a lower score indicating greater disease severity.

MMSE score will be analyzed by MMRM, similar to the co-primary endpoint ADAS-Cog11 score.

Change from baseline to Week 12 in DSST

In the DSST individuals are asked to record associations between different symbols and numbers within time limits. The total score is the sum of all the correctly coded numbers and higher scores indicate better performance.

DSST score will be analyzed by MMRM, similar to the co-primary endpoint ADAS-Cog11 score.

As the study is also designed to explore the effectiveness of three buntanetap-treatment dose levels on secondary endpoints, similar MMRM will be applied comparing each buntanetap-treatment dose arm with placebo.

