APPENDIX 1: SCHEDULE OF EVENTS

Study Period	Screening/Baseline	10	At-Home Treatment		Unscheduled Visit ^k	Early Discontinuation Visit
Visit Timing	Day -42 to 0		6 weeks ± 7 days	12 weeks ± 7 days (end-of-trial) ^b		
Procedure	Screening in (up to 42 days	Baseline (Day	Clinic Visit	Clinic Visit	Clinic Visit	Clinic Visit
	before Day 0)	9)	•	•		
Informed consent	X					
Inclusion and exclusion criteria	X	X				
Demography information	X					
Full physical and neurological examination	X	X	×	×	X	×
Height, Weight, BMI	×					
Medical and psychiatric history (includes substance use)	×					
Urine pregnancy test (WOCBP only)	X	X	X	X	X	×
MMSE	X	X		X		×
ADCS-CGIC		X ^d	Xe	Xe		Xe
ADAS-Cog11		X	X	X		X
ADCS-ADL		X	X	X		×
DSST		X	X	X		×
C-SSRS	X	X	X	X	X	X
Safety laboratory tests ^c	X	X	X	X	X	X
12-lead ECG	X	X	X	X		X
Vital signs ^a	×	×	×	X	×	×
Randomization		×				
Genetic sample (ApoE)		×				
Study intervention		Χg	Xh	×		
Study intervention compliance review			×	×		
AE/SAE review	×	×	×	×	×	×

Version 2.0, 27 February 2024

ANVS-22002

ANNOVIS BIO, INC.

Study Period	Screening/Baseline	е	At-Home Treatment		Unscheduled Visit ^k	Early Discontinuation Visit
Visit Timing	Day -42 to 0		6 weeks ± 7 days 12 weeks ± (end-of-tria	12 weeks ± 7 days (end-of-trial) ^b		
Procedure	Screening ^j (up to 42 days before Day 0)	Baseline (Day 0)	Clinic Visit	Clinic Visit	Clinic Visit	Clinic Visit
Concomitant medication review	X	×	X	X	X	X
PK sampling		×		X		
Sampling for blood biomarkers		×		X		
24-hour phone follow-up		× :	×	×	×	×
a Vital piers will include oiting blood property builto to property of the rote	pulpo tomporoturo	5005				

^a Vital sign will include sitting blood pressure, pulse, temperature, respiration rate.

of study treatment will complete the End-of-Trial visit. ^b Participants that drop out before the initial 9 weeks of study treatment will complete the Early Discontinuation visit and participants that drop out after the initial 9 weeks

^cSafety labs should be taken fasted.

d ADCS-CGIC evaluation only.

ADCS-CGIC evaluation and scoring the scale.

 ⁹ Participants are given one pill during the visit after taking pre-dose (0h) blood samples and the pills for the remaining 6 weeks at the end of the visit.
 ¹ Participants are given one pill during the visit after taking pre-dose (0h) blood samples.

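### Do the empty Week 6 MMSE cell and the unstated analysis visit for early-discontinuation values undermine the Week 12 analyses?

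*SAP*

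**What the plan says.** **MMSE.** SAP 8.2.3 gives as its reason for the MMRM: "Since the two co-primary endpoints and secondary endpoints are captured at multiple visits". The model has baseline, treatment, visit and treatment-by-visit, with two post-baseline visits, Week 6 and Week 12. SAP 8.2.8 adds: "MMSE score will be analyzed by MMRM, similar to the co-primary endpoint ADAS-Cog11 score". MMSE stands second in the fixed sequence of secondary endpoints (SAP 8.2.1). The Schedule of Events in each document marks MMSE at screening, baseline, Week 12 and Early Discontinuation, and leaves Week 6 blank. The narratives in Protocol 4.2 and SAP 5 nevertheless list MMSE among the tests done at the clinic visits.

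**Values from people who leave early.** Both schedules mark all five scales at the Early Discontinuation visit. Which visit a dropout attends depends on timing. SAP Appendix 1 says: "Participants that drop out before the initial 9 weeks of study treatment will complete the Early Discontinuation visit". Protocol 4.2 says: "Participants that drop out after the initial 9 weeks will be scheduled for an end of trial visit". The End-of-Trial visit shares the Week 12 column, with a window of 12 weeks ± 7 days. Protocol 10 has no 9-week split; for anyone who stops, "an early discontinuation visit will be completed as soon as possible following discontinuation". SAP 8.8 deals with partial dates, missing ADAS-Cog11 items and a control-based imputation for non-completers. It has no sentence assigning discontinuation values to an analysis visit.

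**The concern.** A two-visit model for an endpoint scheduled at one post-baseline visit looks like a specification error, and on an endpoint in the confirmatory sequence. The clause in SAP 3 that lets the SAP prevail does not settle it, because SAP 5 and SAP 8.2.3 disagree with the SAP's own Appendix 1.

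The second gap reaches both co-primary endpoints. The visit factor has no level for Early Discontinuation, so those scores could be dropped, called Week 6 or called Week 12. If each were called Week 12, scores taken after a few weeks of treatment would dilute the Week 12 effect, and the control-based sensitivity analysis would have almost nothing left to impute. If the choice were made after unblinding, it could be made to suit the result.

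**Working it through.** **1. The plan's own figure.** SAP 6 gives 210 v 70 evaluable, difference 2.7, SD 6.0, two-sided 5%.

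- Standard error = 6.0 × √(1/70 + 1/210) = 0.828.
- 2.7 / 0.828 = 3.26, and 3.26 − 1.96 = 1.30, so power is 90.3%. The stated 90% reproduces.
- The 320 to be randomised follows too: 280 / (1 − 0.125) = 320, "to account for an expected 12.5% dropout rate".

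**2. MMSE with Week 12 rows only.** The visit term then has one level, so it is confounded with the intercept, and treatment-by-visit is confounded with treatment:

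expected change = (intercept + visit) + b × baseline + (treatment + treatment-by-visit) × T.

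The design has 5 columns and rank 3, and the unstructured covariance is a single variance. The Week 12 contrast remains estimable and equals the treatment coefficient of an analysis of covariance. On one simulated dataset both gave 0.8867. If the narratives were right and MMSE were taken at Week 6, the same model would be an ordinary two-visit MMRM. The model as written is therefore valid under either reading.

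**3. How many values the second gap concerns.** Assume dropout uniform over 12 weeks and everyone attending the leaving visit.

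- Dropouts: 0.125 × 320 = 40.
- Before Week 9 (Early Discontinuation visit): 40 × 9/12 = 30.
- After Week 9 (End-of-Trial visit): 40 × 3/12 = 10. Of these, 40 × 2/12 = 6.7 stop in Weeks 9 to 11, before the window opens; they would be assessed outside it only if the visit follows promptly.

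**4. The plain reading by hand.** Early Discontinuation values are not in the model; End-of-Trial values are Week 12. With linear accrual, the 10 late values, at a mean of 10.5 weeks, carry 10.5/12 = 87.5% of the effect.

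- Dilution = 10/290 × 0.125 = 0.43%, so the effect is 2.7 × 0.9957 = 2.688.
- With 72.5 v 217.5, standard error = 6.0 × √(1/72.5 + 1/217.5) = 0.814. Then 2.688 / 0.814 = 3.30, and power is about 91%.
- If Protocol 10 is read literally, all 40 have Early Discontinuation visits and none enter as Week 12. That leaves 280, the 70 v 210 of step 1, at 90.3% with no dilution.

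**5. Simulation.** 4,000 trials per case, 80 v 240, two-visit MMRM with baseline covariate and unstructured covariance, random dropout, visit correlation 0.5 (assumed).

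| What counts as Week 12 | Mean estimate | Power | Null rejection |
|---|---|---|---|
| Only values inside 12 weeks ± 7 days | 2.706 | 0.908 | 0.0495 |
| End-of-Trial values (plain reading) | 2.693 | 0.915 | 0.0498 |
| Each value goes to the next scheduled visit | 2.638 | 0.917 | 0.0503 |
| Every discontinuation value | 2.536 | 0.906 | 0.0488 |

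Monte Carlo standard errors are about 0.005 on power and 0.0035 on the null rates. The plain reading lies within 0.5% of the strict window (0.013 / 2.706).

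**6. The last row by hand.** Values before Week 9 have a mean time of 4.5 weeks. Dilution = 30/320 × (1 − 4.5/12) + 10/320 × (1 − 10.5/12) = 5.86% + 0.39% = 6.25%. Almost all of it comes from calling Early Discontinuation values Week 12.

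**7. The sensitivity analysis.** Week 12 values left to impute: 40 − 10 = 30 on the plain reading, about 37 under a strict window, and 40 if Protocol 10 is read literally. The imputation is emptied only by the last row of the table.

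**The case for a change.** The best case for a change is that the SAP is silent on both co-primaries and other parts of it touch the gap. A participant whose only post-baseline score is from Early Discontinuation qualifies for the modified intent-to-treat set but has no level of the visit factor. The per-protocol set admits 67 days of exposure, while the Week 12 window opens at 84 − 7 = 77 days. The strict window and the all-as-Week-12 rule disagree on significance in 4.5% of simulated trials (2.7% under the null). Picking the best of four mappings after unblinding would raise the error on one endpoint from 5.0% to 6.7%. For MMSE, an illustration with assumed inputs changed the 5% verdict in 9.9% of trials when Early Discontinuation scores were called Week 12.

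The omission is real, but the consequences do not follow. The 4.5% and 9.9% figures both need Early Discontinuation scores to be labelled Week 12, although both schedules give that visit its own column and SAP 8.8 treats non-completers' later data as missing. The 6.7% needs selection after unblinding, which nobody proposes, and it is not the trial's error rate, because SAP 8.2.1 requires both co-primaries. A participant with no level of the visit factor adds no row to the MMRM and affects only the reported count. The 67-day threshold suggests the SAP accepts a Week 12 analysis of people who stop somewhat early.

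A strict-window rule brings no gain in power or error control. Combined with a Week 6 assignment for MMSE it would cause a difficulty of its own: nobody would have both visits, so the covariance between them could not be estimated. The Week 12 MMSE estimate would still barely move (0.888 against 0.887 in the simulated trial).

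**Conclusion.** No change to the plan follows. The Week 6 MMSE mismatch is a clerical slip between narrative and schedule, and alone it changes no estimate: the model fitted is the right one whichever text is correct. The missing visit assignment is a gap that analysts would fill sensibly from the layout of the schedules. Filled that way, it costs about 0.5% of the ADAS-Cog11 effect relative to a strict window, with power near 91% and error at 5%. The difference in Protocol 10 over which visit late leavers attend is an inconsistency to reconcile as housekeeping; either version keeps power at or above the planned 90%.

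This rests on uniform dropout at 12.5%, full attendance at the leaving visit, linear accrual of effect, a visit correlation of 0.5, dropout unrelated to outcome, and visit labels being settled before unblinding, as is usual. Lower attendance makes the choice matter less: even under the all-as-Week-12 rule the dilution falls to about 3.3% with half attending (15/300 × 0.625 + 5/300 × 0.125), and to 0 with none.
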